- **Fidelity Protocol:** The fidelity of the text-message component is assured, as all text-messages will be automated. To assess fidelity of in-person ED sessions, all will be audio-taped. The interventionist's first 10 tapes will be rated by Drs. [name] and [name], *according to guidelines to be developed in Aim 2*, to objectively evaluate if there is protocol drift. If tapes meet the 80% criterion, 20% of recordings thereafter will be coded. Criteria for adherence to the ED session will be defined in terms of specific content areas, as well as adherence to basic CBT and MI principles.[49-51] **This will serve as a training activity.**

- **Incentives:** Maximum compensation for completion of the entire trial will be \$150 (\$25 for baseline, \$40 for 8-week follow-up, \$50 for 16-week follow-up, \$20 for unlimited text-messaging plan for 8 weeks, \$5 for alerting us to a change in phone number, \$5 each for finishing the 8 & 16 week follow-ups online). [name] and [name] have successfully recruited and retained 80-90% of participants for 12-month follow up across multiple trials with high-risk adolescent ED patients, using similar protocols and compensation.[42, 47, 89]

Mental Health Safeguards and Data Management: The research assistants will be extensively trained by the PI and Mentor [name] to recognize and manage participant distress. In case of severe depressive symptoms, suicidality, or other crises during in-ED screening, the interventionist will immediately notify the PI and the attending emergency physician. If mental health crises are identified during interviews outside the ED, the research team will contact the PI at time of identification and refer appropriately, according to the drafted crisis plan. Mentor [name], a licensed clinical psychologist, will be available by phone for clinical decision-making. Please see **Human Subjects** for further details.

STATISTICAL ANALYSIS

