- Sample size: For this intervention pilot study, we chose to recruit 120 subjects in the RCT. Conservatively estimating that 20% may be lost to follow-up, 96 subjects will complete the 16-week assessment. This number will be sufficient to allow us to make judgments regarding feasibility and acceptability. Despite problems in the stability of effect size calculations with small samples, if a small effect size is detected between groups, and the intervention is shown to be feasible and acceptable, then further testing in a larger trial may be indicated given the innovative nature of the intervention and its potential disseminability.[138, 139] Based on our Aim 1 results, we anticipate that the mean PHQ-9 score of our participants will be 10.0, with a standard deviation of 4.5. If we wish to show a delta-PHQ9 of 2 (with alpha 0.05 and beta 0.8), we would need to successfully follow up 63 participants.

- Data management: Data from text messaging, including time of delivery and any participant responses, will be stored in a de-identified database on a HIPAA-compliant server. This de-identified data will be imported into Stata 12 (Stata Corp, College Park, TX), with which I and my mentors are skilled. Stata 12 is suitable for the multi-level modeling necessary for a fully-powered longitudinal study.

- Acceptability and feasibility (Aim 3a): *Acceptability* will be measured using descriptive analysis of enrollment rates, participants' ratings of the clarity and structure of the in-person and text-message sessions, Client Satisfaction Questionnaire-8,[48] *Feasibility* will be measured using percent of in-person sessions completed, the RSC (as described in Aim 2).[127, 128] and therapist adherence ratings.

- Exploratory hypothesis testing: We will calculate total scores for depressive symptoms (PHQ-9, BDI-II) and violence exposures (CTS-2, CADRI) at baseline and follow-up. We will calculate descriptive statistics for study sample demographics, baseline mediators/moderators (e.g. IPAS, hopelessness), co-morbidities (CPSS) and service utilization (CASA). T-test and chi-square comparisons will be used to detect baseline between-group differences.

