During recruitment, research staff will inform the subject of the general nature of the study, their privacy rights, expectations for their participation, the voluntary nature of their participation, and that their participation can be withdrawn at any time. Participants will be assured that refusal to participate will not affect their care in any way. At all times, research staff will make explicit the voluntary nature of the subjects' participation as well as potential situations for breaking confidentiality. Recruitment procedures will be HIPAA compliant and have been IRB approved in past studies.

Referrals. All participants in the screening will receive a handout of mental health and violence prevention resources. If an adolescent screens positive for severe depressive symptoms at any time during the study, regardless of eligibility for the study, the RA will discuss the score with the family, notify the attending pediatric emergency physician, and offer to contact the adolescent's pediatrician.

If an adolescent discloses suicidality or if the patient's family so desires, the RA will alert the patient's clinician (if appropriate) who will immediately initiate a psychiatric evaluation in the ED, or will contact the patient and his/her parent if disclosure occurs outside of the ED. (See "Mandatory Reporting & Crisis Management," below). If a patient is deemed to need psychiatric hospitalization based on the screening, they will be withdrawn from the study.

Assessments and Remuneration. In **Aim 2**, participants will complete a baseline assessment, an 8-week follow-up assessment and interview; in **Aim 3**, participants will complete a baseline assessment, an 8-week interview and an 8-week and 16-week computerized follow-up assessment. Follow-up assessments will take place online, on the telephone, or in private rooms at the PI's departmental office (separate from the ED) where privacy and confidentiality can be maintained (i.e., making sure no one can overhear the conversation).

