- (c) The only list connecting the participant ID # to the participants' names will be kept in a password-protected folder on the PI's password-protected computer (which is owned by the hospital, and which is on the hospital's HIPAA-secured research server). This list will be deleted as soon as each phase of the study is completed.
- (d) The consent forms and research materials will be kept in separate double-locked cabinets in the PI's locked office.
- (e) All computerized information will be maintained on password protected, HIPAA-compliant computers owned by the PI's hospital which use only HIPAA-compliant research server.
- (f) All computerized surveys will be completed using REDCAP.
- (g) No names, only identification codes, will be used in presenting data in lectures, seminars, and papers.

SEMI-STRUCTURED INTERVIEWS:

- (a) Semi-structured interviews will take place in a private room at the site of the participant's choosing (e.g. ED, PI's departmental office, library, telephone) where confidentiality can be assured

- (b) Ground rules will be set at the beginning of the interviews, instructing participants to not identify themselves or others by name, and emphasizing the confidentiality of everything discussed [with the exception of suicidality/homicidality/child abuse].
- (c) Participants will be not be referred to by name on the audiotapes.
- (d) Prior to transcription, the digital tapes will be kept in a password protected format on a password-protected Lifespan hard-drive accessible only to the PI and the RA. The recordings will be maintained for 5 years in compliance with human subjects policies.
- (f) Transcripts will be reviewed only by the PI and her research team.

TEXT-MESSAGING:

- (a) All text-messages will be sent using a secure text messaging system (hosted by Reify Health, a company that we have worked with in the past for similar projects) that will not store data remotely; the text-message server is located behind a research-compliant firewall.
- (b) Text-message data will be maintained in a password-protected, restricted-access hard drive in the Department of Emergency Medicine.
- (c) Text-message data will be monitored exclusively by the PI and her research team.

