Participant confidentiality will be breached only to protect the safety and welfare of research participants and only in accordance with state and federal law. The exceptions to confidentiality include if the adolescent reports suicidality, homicidal thoughts, or that he/she is the victim of child abuse or neglect. If the adolescent reports suicidality or homicidality, parents will be notified, and an emergency psychiatric evaluation for inpatient hospitalization will be facilitated with the Pediatric Emergency Psychiatric Service at Rhode Island Hospital. If necessary, authorities will be notified. If child abuse or neglect is reported, a report will immediately be filed with the Department of Children, Youth and Families. This exception to breaking confidentiality – the case where a participant reveals child abuse, suicidality, or homicidality – will be explained in detail to both participants and parents prior to completing the assent/consent.

Finally, information collected in this research study will not be available to clinicians, parents, or to other researchers. All data will be collected specifically for use on this project.

Risk 3) Emotional Discomfort

Of note, members of the proposed mentorship team have substantial prior clinical and research experience with high-risk populations as evidenced through their biographical sketches. [name] has extensive clinical and research experience developing interventions for depressed, suicidal, and alcohol-abusing adolescents. [name] has extensive clinical and research experience with adolescent violence and substance abuse prevention.

Parental distress: If parents report feelings of distress as a result of being notified that their child is eligible for this research project, clinical resources will be offered. These include referrals for mental health counseling and information about violence hotlines and local community organizations.

Assessments: The assessment instruments are commonly used in research and clinical practice. We will minimize distress by presenting questions/program techniques in a supportive manner, assuring participants that they may refuse to answer questions that make them uncomfortable, and reminding them that they may terminate the assessment and/or intervention at any time.

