Although there is extremely low risk of an adverse reaction to the screening survey or qualitative interviews (and, in fact, benefits to participation in similar research have been demonstrated),[151] all potential participants will be provided with a list of community resources at the same time that they are approached by the RA about participation in the study. To minimize negative consequences from the screening survey or semi-structured interviews, the RA will be trained to immediately terminate the assessment and alert the PI and the patient's clinician in the case that the subject demonstrates physical or psychological instability.

Additionally, on completion of baseline and follow-up assessments, the RA will be alerted by the computer if a participant has reported suicidality or severe depressive symptoms. The RA will contact [name] or [name] at that time, and the teen will be further evaluated for risk of harm to self or others. To the extent that the adolescent is determined to be a risk to himself/herself or others, the parent will be notified and a referral to an emergency evaluation with the Pediatric Emergency Psychiatric Service at Rhode Island Hospital will be made.

Regarding the text-messaging component of the study, text message assessments do NOT induce depression despite repeated assessments of negative mood.[152] Momentary assessments have also been shown to be acceptable, feasible, and appropriate when used to ask sensitive assessments (e.g., suicidality,

mood, alcohol and substance use, eating disorders, and violence) among a variety of populations, including school-age adolescents, schizophrenics, the homeless, drug addicts, recently hospitalized suicidal patients, and college students.[153-163]

Text-message Data: Participants and parents will be explicitly instructed during the consent process that no one will be monitoring text-message data in real time. In the case of a crisis situation, the adolescent should call the provided crisis hotline number or the PI's phone number rather than text the program. Nonetheless, some participants may misinterpret these guidelines. Hence, text-message data will be reviewed regularly by the PI and her mentorship team. The software will also be designed to send participants a message that directs them to a crisis phone number, if data that is not expected by the text-message algorithm is received.

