That said, we will be clear during the assent/consent process with the parents and child that we will not be conducting ongoing, real-time monitoring of the text messaging. We will emphasize that if a child needs immediate assistance, s/he or his/her parents should call 911, the child's doctor, or call one of the crisis numbers provided.

By notifying parents/guardians of the teen's risk, providing parents with the information they need to monitor their child's risk, and by conducting ongoing monitoring of the safety of the teens, **we are maintaining the highest ethical standard for our participants.**

Risk 4) Violence

The emergence of increased aggression is important and needs to be monitored. If a subject discloses increasing frequency of involvement in violence, severe physical injury, homicidality, or high risk of retaliatory violence she will be contacted by the PI for further evaluation. Although no questions will be specifically asked about child abuse or sexual assault during the study, the staff will be trained to assess and respond to participants for whom these issues arise.

Risk 5) Mandatory Reporting and Crisis Management:

As described above and in the Data Safety & Monitoring Plan, below, all instances of potential mental health or violence risks, staff will follow a written protocol regarding reporting these incidents to [name] or [name] based on call schedule, and will take appropriate referral or legal action as indicated. In addition, the IRB board at Rhode Island Hospital will be informed of any incidents. Drs. [name] and [name] will be responsible for providing training to all research staff who are conducting assessments with participants regarding procedures for identifying, managing, and responding appropriately to acute warning signs of distress that could occur as a result of the survey. Such strategies include maintaining an empathic response, acknowledging the distress through reflection, and eliciting or encouraging use of relaxation and cognitive

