As additional safeguards, **if a child reveals substantial mental health problems, such as suicidal ideation/attempts, homicidal ideation, or clinical deterioration, or if such problems are identified during the course of the study**, the child will be evaluated as soon as possible, by the PI, the primary mentor, and (if indicated) the on-call RIH psychiatric crisis team, to make a clinical determination about whether the child requires hospitalization or other clinical services. The primary mentor is a licensed child clinical psychologist and has training and experience in intervening in similar crisis situations. Project staff will carry cell phones with them during all participant contact and will be instructed to contact the PI (who is on call and always carries a phone) immediately to inform her of any clinical emergency. Additionally, [name] and [name] will carefully monitor the symptom progression of all participants. **If a patient is deemed to need psychiatric hospitalization based on the screening, they will be withdrawn from the study.**

If any mental health problems are reported or identified at the time of the follow-up and the family is not in treatment, appropriate referral for psychological intervention will be arranged.

Whenever possible, study staff will handle these situations therapeutically. For example, if time limits and safety concerns allow, parents will be informed in advance and provided the opportunity to participate in the mandated report process. Research staff will contact the PI who will be responsible for any on-site clinical decision-making.

Over the past 10 years, in several ED studies conducted by myself and my mentors, staff have encountered only 2 cases of harm to others that involved crisis management procedures leading to breaching confidentiality and involving authorities, less than 10 cases of child abuse requiring mandatory reporting to the police, and regular suicide risk assessments (~10 participants per study, per month).

14c. Potential benefits of the proposed research to the subjects and others:

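### The stated suicidality alert fires only on completion, so an online 8- or 16-week survey abandoned after a suicidality answer has no stated prompt detection step

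*Combined protocol and SAP*

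**What the plan says.** The alert is in section 14b.2, Risk 3 (Emotional Discomfort): "on completion of baseline and follow-up assessments, the RA will be alerted by the computer if a participant has reported suicidality". The same sentence covers severe depressive symptoms. The research assistant is then to contact one of two named senior team members straight away, and the teen is evaluated for risk of harm.

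Section 14b.1 (Assessments and Remuneration) sets the mode of follow-up: "Follow-up assessments will take place online, on the telephone, or in private rooms". The Aim 3 Incentives paragraph attaches a $5 payment to finishing each of the 8- and 16-week follow-ups online, although section 14b.1 ties that payment to finishing before the due date. Section 14b.2 also says that distress will be limited by, among other things, "reminding them that they may terminate the assessment and/or intervention at any time".

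On the software, section 14b.2 (Risk 2) says "All computerized surveys will be completed using REDCAP". It does not say how unfinished records are stored or whether single items can raise an alert.

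Two operational documents are mentioned but not reproduced. Under Mental Health Safeguards and Data Management, staff who identify a crisis in an interview outside the ED are to contact the PI and "refer appropriately, according to the drafted crisis plan". Under Risk 5, "staff will follow a written protocol regarding reporting these incidents".

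**The concern.** Three provisions, each reasonable alone, leave a gap together: the alert waits for completion, the survey may be taken with no staff present, and the teen is told that stopping is allowed. Assessments are expected to take about 30 minutes, so an unfinished online survey is foreseeable as well as permitted.

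What is at stake is the response the plan promises to a minor who reports suicidality. That response is immediate staff contact and risk evaluation (Risk 3), and parent notification with an emergency psychiatric evaluation (end of Risk 2). The Risk 2 commitment depends on the adolescent reporting suicidality, with no condition that the survey be finished. The alert that would set it in motion is therefore narrower than the commitment.

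Teens with some suicidal ideation can be enrolled. Apart from an acute-suicidality chief complaint at screening, the related exclusions are severe depressive symptoms and a clinician's judgement that psychiatric hospitalization is needed. A positive answer to the ideation question leads to physician notification and does not by itself exclude.

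**Working it through.** The plan gives no figure to reproduce, and the claim depends on no power or sample-size quantity. The check is whether any stated step would promptly find a suicidality answer in an unfinished online follow-up.

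**Safeguards set side by side**

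| Where | What it provides | Does it promptly find the answer? |
|---|---|---|
| 14b.2 Risk 3, computer alert | Alert on completion | No; an unfinished survey does not reach the trigger |
| 14b.2 Risk 3, research assistant stops the assessment and alerts | Tied to the screening survey and semi-structured interviews | No; needs staff present |
| Mental Health Safeguards and Data Management | Crises identified during interviews outside the ED | No; limited to interviews |
| 14b.1 Referrals; end of Risk 2; Ongoing Safeguards | Response once suicidality is disclosed or seen | No; these are response duties |
| 14b.2 Risk 5, named team members "will carefully monitor the symptom progression of all participants" | General monitoring | No schedule, data source or mention of unfinished surveys |
| Aim 2, Text component | Weekly review of text responses | No; covers texts, not surveys |
| 14f, weekly meetings | Progress, data quality, retention, participant experiences, adverse-event rates | Not stated to cover individual survey answers, and weekly at best |
| Ongoing Safeguards, PI and crisis numbers | Given to every participant | Only if the teen calls |

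No row supplies the missing step. For text messages, by contrast, the plan expects that some teens will misunderstand the rules. It therefore adds regular review and an automatic crisis message after unexpected input. Nothing similar is stated for an abandoned survey, where suicidality is one of the things the alert is meant to pick up.

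**Ceiling on exposure**

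Inputs: two follow-ups per participant (8 and 16 weeks, Table 11.3). For the number randomised, the Sample size paragraph says "we chose to recruit 120 subjects in the RCT", while the Aim 3 randomisation paragraph and section 14a.1 give 50 per arm.

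- Scheduled follow-ups = participants × 2
- With 120 randomised: 120 × 2 = 240
- With 50 per arm: (50 + 50) × 2 = 200

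These counts cover all modes, before any loss to follow-up. The number affected is a subset that needs online mode, a suicidality answer, and abandonment after that answer without returning to finish. For the answer to be recoverable, it must also have been saved. The documents give no online share, abandonment rate or item order (Table 11.3 lists instruments only), and do not say whether partial answers are kept. No estimate of affected teens and no bound on the delay can be derived.

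Baseline takes place in the ED, and telephone or office follow-ups involve staff, so these are outside the point.

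**The case against.** The strongest reply is that the evidence is incomplete. The survey build, crisis plan and written reporting protocol are where an item-level trigger would normally be set out, and none is available here. The alert sentence does not say that completion is the only trigger, and it may be loose wording for the time of the assessment. Elsewhere the duty to act follows from any disclosure or sign of suicidality, so the plan is unlikely to intend that a partial answer be ignored.

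There is also more human oversight than the alert sentence suggests. Weekly meetings cover retention and data quality. The online payment implies that staff track who finished. Some teens have an 8-week interview, though qualitative interviews are limited to at most half of each group. The payments of $40 and $50 for the two follow-ups may keep abandonment low. If the suicidality item comes last, few or no teens would be affected.

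Much of this stands. The unseen documents are a real limit, the frequency may be very small, and an unfinished survey might well be noticed in time. None of it supplies prompt detection, however. Knowing that a survey is unfinished is different from reading the suicidality answer in it. A duty to respond to a disclosure does not show how the disclosure is found.

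**Conclusion.** The concern holds in its narrow form. The only computer alert the documents state is tied to completion. Followed as written, it misses a suicidality answer in an online 8- or 16-week survey that a teen leaves unfinished, and no other stated step would find that answer promptly.

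The size is unknown. It cannot exceed the 240 (or 200) scheduled follow-ups, and it may be few or none. The conclusion assumes that completion means finishing the survey, and that the unseen survey build and crisis plan add no earlier trigger. Confidence is therefore medium. The change is still worth making, because a late response to a minor's report of suicidality is serious and the correction is cheap. Outcomes, analysis and randomisation are not affected.

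**What to change.** First, confirm whether the survey build or crisis plan already raises an alert on unfinished online surveys. If it does, only the sentence in 14b.2 needs rewording to say so.

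If it does not, then for the 8- and 16-week surveys:

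- trigger the suicidality alert when the item is saved or its page is submitted;
- include partial records in the alert check;
- keep the severe-symptom alert on the finished scale, where the score is defined;
- leave the response pathway unchanged;
- reword the alert sentence in 14b.2 (Risk 3) to match.

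The cost is survey configuration, one reworded sentence and a few extra alerts to review, some from teens who later return and finish. This assumes that the survey software can save partial answers and alert on a single item, which the documents do not state. Staff would also be acting on answers from teens who chose to stop. The consent process already explains that reported suicidality is an exception to confidentiality, but it should be checked that this explanation extends to answers saved in an unfinished survey.
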